Few lifestyle behavior change interventions have been successfully translated into practice. Addressing this research-to-practice gap is a significant research and public health priority. “Harvest for Health” is a home-based vegetable gardening intervention that pairs cancer survivors with certified Master Gardeners from the Cooperative Extension System. The parent study was started at the University of Alabama at Birmingham and is currently being conducted throughout the entire state of Alabama. Preliminary findings suggest that this intervention increases vegetable consumption and physical activity, and improves physical functioning and health-related quality of life. We propose a feasibility study to adapt this promising program to the multi-cultural population of cancer survivors and for the local context (physical, social, and cultural environment) of New Mexico. We will then implement the adapted program, “Southwest Harvest for Health” and evaluate feasibility, acceptability, and fidelity. The adaptation phase is a critical first step towards widespread dissemination, implementation, and scale-up of an evidence-based intervention. Results from this feasibility study will be used to inform a larger, definitive R01 study with statistical power to assess the efficacy of the program in the culturally, geographically, and socioeconomically diverse population of cancer survivors throughout New Mexico.

Objectives

Specific Aims

“Harvest for Health” is a home-based vegetable gardening intervention that pairs cancer survivors with certified master gardeners (MGs) from the Cooperative Extension System, the education and outreach arm of land-grant universities nationwide.¹⁻⁵ Preliminary results suggest that this intervention increases vegetable consumption and physical activity, and improves physical functioning and health-related quality of life (hrQoL).¹⁻³ The “Harvest for Health” program has tremendous potential for sustainability, and widespread dissemination and implementation since MG programs exist in all 50 United States.^{6,7} To date, it has been tested in primarily non-Hispanic white cancer survivors living in Alabama. We propose a pilot study to adapt this promising program to the multi-cultural population of cancer survivors and for the local context (physical, social, and cultural environment) of New Mexico. We will then implement the adapted program, “Southwest Harvest for Health”, and evaluate the feasibility and acceptability through a pilot study taking place in Bernalillo and Southern Sandoval Counties in New Mexico. Our transdisciplinary research team is well-poised to pursue the following specific aims:

Aim 1: Adapt the “Harvest for Health” intervention to the drastically different climate and growing conditions, and the multi-cultural population of New Mexico using a recommended adaptation framework.^{8,9}

Aim 2: Assess the feasibility and acceptability of the “Southwest Harvest for Health” program through recruitment and retention rates, adherence/fidelity to the intervention, and acceptability of the program for both cancer survivors (participants) and Cooperative Extension Master Gardeners (volunteer mentors). We hypothesize that we will be able to

PROTOCOL TITLE: Southwest Harvest for Health Pilot

recruit 25-30 cancer survivor / MG dyads (based on similar geographic location) within 6 months, retain >80% of the sample, and achieve 80% adherence/fidelity to the protocol and intervention. We also hypothesize that we will receive positive feedback on the mentored vegetable gardening program from both participants and MGs.

Aim 3: Obtain estimates on pre-post changes in secondary endpoints including vegetable servings per day, physical activity, sleep quality, physical functioning and performance, and hrQoL.

Aim 4: Conduct a process evaluation using qualitative and quantitative measures to inform a larger definitive trial

The proposed study is an excellent opportunity to help grow the “Harvest for Health” program and reach a greater number of cancer survivors. The adaptation phase is a critical first step towards widespread dissemination, implementation, and scale-up of an evidence-based intervention. Results from this pilot study will be used to inform a larger, definitive R01 study with statistical power to assess the efficacy of the program in the culturally, geographically, and socioeconomically diverse population of cancer survivors throughout New Mexico (e.g., PAR-18-869, PA-18-385).

1. Background and Significance

By 2022, there will be 18 million cancer survivors living in the U.S.¹⁰ Cancer survivors are at increased risk for treatment-related comorbidity, including cardiovascular disease, diabetes, osteoporosis, impaired physical functioning, and reduced hrQOL.¹¹⁻²⁰ A healthful diet and regular physical activity may help prevent, delay or mitigate poor health outcomes associated with cancer and its treatment. While a cancer diagnosis is considered a “teachable moment” for improving lifestyle behaviors,²¹ a large proportion of cancer survivors do not adhere to guidelines for a healthy lifestyle.²²⁻²⁴ While many lifestyle interventions conducted among cancer survivors have demonstrated efficacy in improving diet, physical activity, or quality of life, the long-term durability of these interventions remains unanswered, and the potential for widespread dissemination for many of these center- and clinic-based programs is limited.

Emerging data suggests that vegetable gardening may provide an integrated approach to promote a healthful diet, physical activity and functioning, stress relief, and psychosocial well-being.^{1-3,25-29} Furthermore, gardening has great potential for sustainability given its holistic nature and wide range of benefits. The variety of gardening activities and tasks may prevent boredom, which is common with other exercise programs and can jeopardize adherence long term.³⁰ Additionally, gardening may provide a sense of accomplishment and an increased satisfaction and quality of life that comes from nurturing and observing new life and growth. More importantly, gardening provides natural motivation since plants require regular care (watering, pest control) and attention (harvesting) and serve as continual and dynamic behavioral cues.

PROTOCOL TITLE: Southwest Harvest for Health Pilot

The “Harvest for Health” program utilizes the infrastructure of the Cooperative Extension MG Program.^{5,7} The MG Program, one of many educational outreach programs offered in each US state by the National Institute of Food and Agriculture through the Cooperative Extension System, recruits and trains volunteers to help disseminate research-based information on landscaping and gardening to the general public. Certified MGs complete >60 hours of training and community service, with many states requiring additional volunteer service (e.g., >40 hours) annually to maintain active status. Based on studies conducted in Alabama,¹⁻³ “Harvest for Health” has been a popular and rewarding volunteer experience for MGs.¹⁻³ The MG program exists in all 50 US states and thus provides the capacity for sustainability and wide-spread dissemination. With minor adaptions (e.g. cold framing) for colder climates with only two growing seasons, this intervention could be implemented in 72% of US states. Furthermore, these programs typically have wide-spread coverage throughout the state, thus allowing both urban and rural individuals the opportunity to participate.

2. Study Design

As this is a small feasibility study, a single-arm study design will be employed, where all participants receive the 10-month mentored vegetable gardening intervention at their homes. Therefore, given a single arm pre-post intervention design, blinding of study participants and study staff is not applicable. The focus of this pilot study is to systematically identify, document, test, and evaluate the adaptations needed for the “Harvest for Health” program to be successfully implemented in New Mexico. Using the NCI Research-tested Intervention Programs (RTIPs) adaptation guidelines, we will identify changes needed for our population and local context, while maintaining fidelity to the original intervention (see Table 1).^{8,9}

Table 1. Key Steps for the Adaptation of “Harvest for Health” to “Southwest Harvest for Health”		Status
Adaptation	Description	
1. Assess Community	
• F&V intake, physical activity, & hrQOL are low in many NM cancer survivors• Bernalillo County MG Program has the capacity to provide & support MG volunteers for the study (>300 active MGs; based on discussions/meetings)	
	
• Harvest for Health intervention materials have been shared• Theory behind program is understood & core elements have been identified	
3. Consult w/ Experts	
• Consult with [name] (developer of original program) and local MG Program experts (currently underway)• Incorporate expert advice into new program	
	
• Determine how original & new target population/context differ• Identify potential ways to implement new program• Retain fidelity to core elements of original program• Document the process from the beginning (for later evaluation)	
4. Decide what needs adaptation		

PROTOCOL TITLE: Southwest Harvest for Health Pilot

5. Adapt original program	
• Work with consultant to ensure adapted procedures/materials maintain accuracy of originals• Make cultural adaptations continuously	
6. Train staff	
• Recruit and train MGs and staff to ensure quality implementation	
7. Implement	
• Implement program (25-30 cancer survivor / MG dyads, 3 gardening seasons)	
8. Evaluate	
• Evaluate the process & outcomes of adapted program (e.g., fidelity, barriers & facilitators to implementation) using the RE-AIM evaluation framework ³¹• Modify adapted program based on feedback (for evaluation of effectiveness in a larger trial, i.e., R01 trial, before moving to D&I on a larger scale)	

3. Inclusion and Exclusion Criteria

Screening

Passive recruitment methods will be used for this small, feasibility study. Recruitment flyers will be distributed in community locations such as libraries, grocery stores, community centers, senior centers, and cancer survivor support groups in Bernalillo and South Sandoval counties. Additionally, oncologists or physicians may refer their patients (cancer survivors) to the study by giving them a study flyer. Faculty and staff from the Division of Epidemiology, Biostatistics, and Preventive Medicine and the UNM Comprehensive Cancer Center will be emailed a copy of the study flyer, provided approval from leadership (i.e., Division Chief, Associate Directors or Program Leaders). The email will briefly explain the study, and indicate a \$5 gift card for one of UNM HSC campus coffee shops will be provided for anyone referring an individual to the study, regardless of final eligibility (referred individual must contact study staff).

Cancer survivors interested in participating will contact a member of the Southwest Harvest for Health (SWH4H) study team. The screening will take place by telephone. The study coordinator/recruiter will provide additional information about the study, answer questions and assess eligibility using the study recruitment script.

Inclusion Criteria

Twenty-five adult (50 years and older) male and female cancer survivors residing within Bernalillo and southern Sandoval County will be recruited for this study. Additional eligibility criteria include:

- Diagnosed with an invasive, non-metastatic cancer; metastatic cancer patients are eligible with MD written or verbal approval
- Completed primary treatment (surgery, radiation, chemotherapy); note that endocrine therapy is allowed.
- Able to read, speak, and understand English. (The future larger trial will include Spanish-Speaking participants)

PROTOCOL TITLE: Southwest Harvest for Health Pilot

- Not told by a physician to limit physical activity and no pre-existing medical condition(s) that would preclude gardening, e.g., severe orthopedic conditions, hip or knee replacement surgery within 6 months), end-stage renal disease, paralysis, dementia, blindness, unstable angina, untreated stage 3 hypertension, or recent history of myocardial infarction, congestive heart failure, or pulmonary conditions that required oxygen or hospitalization within 6 months.
- Community dwelling and not residing in a skilled nursing or assisted living facility (must be able to tend to their garden and cook their own meals).
- Residing within 30 miles of one of the Master Gardener volunteer mentors
- Currently not adhering to the recommended number of fruit and vegetable servings per day (consuming fewer than 5 servings of vegetables and fruits/day and not meeting the recommended guidelines for moderate-to-vigorous physical activity (< 150 minutes/week)
- Reside in a location that can accommodate a 4' x 8' raised garden bed or 4 (29" x 14") garden containers, or adequate (at least 4 hours) of sunlight per day and have access to running water
- No existing or recent (within the past year) experience with vegetable gardening
- Able to participate in the 10-month intervention (all three seasonal gardens; roughly from mid-February through early November 2020)

Exclusion Criteria

Individuals will be excluded from participation if they:

- Are not able to consent
- Are not competent due to mental health or other very serious comorbid conditions (e.g., stroke, degenerative neurological conditions)
- Have any medical condition that substantially limits daily light-intensity physical activity (i.e. activities of daily living: bending, stooping, walking, etc.)

Also excluded from participation in the proposed study:

- Due to the focus on older cancer survivors, individuals who are not yet adults (infants, children, teenagers) or who are considered adolescent and young adults (ages 15-39) will be excluded from this study. In the future, this study may be adapted to suit adolescent and younger cancer survivors.
- Given the focus on older (50+ years) cancer survivors, women who are pregnant or who are planning to become pregnant, will be excluded from this study.
- Prisoners may not participate in this study as this is a home-based gardening intervention and we are seeking participants who are able to pursue lifestyle changes independently and not as the result of institutional control

Note: Verification of adequate space, sunlight, and running water to support a vegetable garden will occur at the baseline home visit. If these criteria are not met, then the individual

PROTOCOL TITLE: Southwest Harvest for Health Pilot

is not eligible to participate and will receive a \$20 merchandise card for their time. Note that this assessment will take place before any further collection of data.

4. Number of Subjects

The proposed study will enroll 25 to 30 cancer survivors. This study has proved to be very popular, and with multiple recruiters, we reached our original accrual goal of 25, and now have a waitlist. We would like to allow an additional 5 participants (30 maximum).

5. Study Timelines

The proposed grant period is two years with the actual intervention being 10 months (plus or minus 14 days due to scheduling difficulties). Recruitment will occur over a four month period, beginning November 2019. Enrollment of 25-30 participants will be completed by late February/early March 2020. All participants are expected to begin the intervention at the same time (plus or minus 10 days to account for weather and/or scheduling conflicts between the Master Gardener and the participant). The proposed intervention is expected to begin in early March 2020 and end in mid-November 2020, coincident with three gardening seasons (spring, summer, and fall). Data analyses will be completed before March 2021.

Study Timeline: August 2019 – July 2021																		
	2019				2020										2021			
Month	A	N	J	F	M	A	M	J	J	A	S	O	N	D	J	M	M	J
-	-	O	D												-	-	-	
Development																		
Recruitment																		
Intervention delivery																		
Data cleaning/prep																		
Analyses																		
Publications																2		
Grant Submissions																	4	

¹ Study protocol paper

² Study outcomes paper

³ Initial R01 submission

⁴ Revised R01 submission

6. Study Endpoints

Primary and secondary study endpoints

The primary aim is to adapt the Harvest for Health intervention to the multi-cultural population of cancer survivors and for the local context (physical, social, and cultural environment) of New Mexico. The endpoint is systematic documentation of the adaptation process using a recommended framework.

Other endpoints are to assess the feasibility and acceptability of the “Southwest Harvest for Health” mentored gardening program through recruitment and retention rates, adherence/fidelity to the intervention, and acceptability of the program for both cancer survivors (participants) and Cooperative Extension Master Gardeners.

Secondary endpoints include estimates on pre-post changes in vegetable servings per day, physical activity, sleep quality, physical functioning and performance, and hrQOL. Pre-post change data will inform the sample size for the future, larger study.

Primary and secondary safety endpoints

Gardening could result in cuts or scrapes which could expose the participant to bacteria in the soil or exacerbate lymphedema. Cancer survivors for whom gardening activities could pose excess risk will be excluded from the study.

Additionally, gardening involves a variety of movements, i.e., bending, kneeling, stooping, getting up and down, and other light-to-moderate intensity physical activity, which could result in soreness, stiffness, and other potential issues (e.g., sunburn) if substantially different than the participants’ normal daily activities. To mitigate these issues, participants will receive a notebook containing information on gardening safety, e.g., protecting knees and back, sun protection, etc.

All adverse events associated with the performance tests will be tracked. The performance tests incorporate movements typically undertaken during normal daily activities (standing from a chair, walking a short distance, sitting on a chair, lifting a light object, etc.), and thus represent tests that are more likely to be safely performed. One or more members of the study team will be present in the participant’s home during the performance tests. Safety checks will be made prior to the performance tests.

Exploratory endpoints

There are no exploratory endpoints.

7. Research Setting

This is a home-based intervention. The garden will be located at the participant’s home. Members of the UNM study team will visit the participant at their home on three separate occasions (baseline, mid-point, follow-up) during the study to assess health behaviors and outcomes. Study staff will also verify inclusion criteria specific to gardening, i.e., absence of an existing vegetable garden, adequate space, sun and running water to accommodate a successful home vegetable garden.

PROTOCOL TITLE: Southwest Harvest for Health Pilot

Recruitment flyers will be distributed in community locations such as libraries, grocery stores, community centers, senior centers, and cancer survivor support groups.

Study staff will be housed in the Cancer Research Facility, where recruitment and screening will take place.

COVID-19 Modifications

Due to COVID-19, the mid-point and final assessment of health behaviors and outcomes will be conducted remotely (i.e., via mailed and telephone-administered surveys) rather than home visits.

8. Resources Available

Study Personnel

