Participants will be asked to wear the activPAL3, an electronic activity monitor, for the objective assessment of sedentary activity and physical activity. The small, thin device (like a patch) will be worn on their mid-thigh (day and overnight) for 7 days

PROTOCOL TITLE: Southwest Harvest for Health Pilot

at the beginning, at 6 months, and at the end of the study. This is not a tracking device. The activity monitor will record general movement (sitting, standing, and stepping) and will enable us to get a better idea of the participant's daily activity and inactivity levels (versus self-report alone). We will also provide participants instructions for applying and removing the monitor. The activPAL3 monitor will be collected during the home visits for additional outcome assessment. Note: The activPAL3 is attached to the thigh using Tegaderm Dressing (a transparent dressing/tape; see Tegaderm Dressing.PDF uploaded under Local Site Documents – Other Attachments).

Mediators

Community-Level: Participant-MG dyads will independently assess the participant's local environment for support of vegetable gardening considering the following factors: 1) availability of garden stores; 2) presence of pests (i.e., insects, deer); 3) neighborhood covenants that impose landscaping restrictions; and 4) sense of belonging with other gardeners in local community.

Interpersonal: We will use the Social Support & Eating Habits (10 items) & Exercise Surveys.

Individual: This assessment will measure the participant's self-efficacy (survivors' beliefs in their ability to maintain a successful vegetable garden).

COVID-19 Modifications

The following modifications will be made to the mid-point and final (post-intervention) assessment of study outcomes due to COVID-19.

The visit by study investigators to the participant's home will be replaced with remote methods (mail and telephone) in order to avoid any in-person contact between members of the study team and participants in an indoor setting.

Due to this change (from home visit to mail/telephone), the following aspects of data collection will also require change:

- Collect self-reported weight
- Skip all objective measures of physical functioning (i.e., physical performance). Note that while some research studies are moving to a remote assessment of physical performance, this study does not have the resources to be able to collect this type of data remotely at this time.

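### Does replacing the follow-up home visits leave physical performance and activPAL3 activity listed as pre-post outcomes with no way to obtain them?

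*Combined protocol and SAP*

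**What the plan says.** Section 6 of the combined protocol and SAP sets out the outcomes in question: "Secondary endpoints include estimates on pre-post changes in vegetable servings per day, physical activity, sleep quality, physical functioning and performance, and hrQOL". Aim 3 repeats the list, including "physical activity, sleep quality, physical functioning and performance, and hrQoL". Neither place carries a COVID-19 note. Section 6 adds that the change data will feed the sample size of the later trial. Section 12.2 gives no power calculation.

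Section 11 plans three assessments: baseline, about 6 months and 10 months. Under Accelerometry, the activPAL3 is worn for 7 days "at the beginning, at 6 months, and at the end of the study", to give a better picture of "daily activity and inactivity levels (versus self-report alone"). On return of the device it says: "The activPAL3 monitor will be collected during the home visits for additional outcome assessment".

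The COVID-19 modifications to outcome assessment in Section 11 cover the mid-point and final assessments only. Of the study team's visit to the participant's residence they say: "home will be replaced with remote methods (mail and telephone) in order to avoid any in-person contact". The sentence then limits this to indoor contact between study team and participants. Next comes the statement that "the following aspects of data collection will also require change", with four items:

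- weight becomes self-reported;
- performance: "Skip all objective measures of physical functioning (i.e., physical performance"), because the study lacks the resources to test remotely;
- the EATS diet screener moves to telephone, with show cards instead of food models;
- the Godin activity questionnaire is given by telephone.

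The monitor is not among the four. The COVID-19 notes in Sections 7 and 8 describe the remote assessments as surveys by mail and telephone.

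**The concern.** Read in order, the document promises something it later withdraws. Anyone taking the endpoints from Section 6 or Aim 3 would expect a pre-post change in physical performance, yet Section 11 rules out any follow-up measurement of it.

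The monitor looks worse because it is not mentioned at all. Follow-up wear is still scheduled, the only stated return route is a visit that no longer takes place, and the list of changed items passes over it. If the devices were never returned, the study would have no objective estimate of change in activity. Physical activity would then rest on the Godin questionnaire alone, although the protocol added the monitor to improve on self-report. A change estimate meant to inform a later trial would be weaker for it.

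**Working it through.** The plan states no number of pairs, no standard deviation and no power, so there is no figure of its own to reproduce. The check is a count, followed by a comparison of the sections.

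**Inputs**
- Enrolment: 25 to 30 (Section 4).
- Retention: at least 80% (Section 12.1; Aim 2 says above 80%). This is a floor, not a forecast.
- Assessments: 3, of which 2 are follow-up (Section 11).
- Monitor wear: 7 days at each of 3 time points (Section 11, Accelerometry).
- Timing: mid-point assessment in August, final assessment in the first week of November (Section 11, intervention schedule). A note in the same section is dated 11/1/2020.

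**Participants available for pairing**
- 0.8 × 25 = 20 and 0.8 × 30 = 24 at the retention floor; 25 to 30 if everyone is retained.

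**Performance**
- Pairs = participants × (measured at baseline, 1) × (measured at follow-up, 0) = 0, at any enrolment or retention.
- Self-reported physical functioning can still be paired, because PROMIS-57 has a physical function domain and can be completed remotely.

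**activPAL3**
- Follow-up wear periods per participant: 3 − 1 = 2.
- Follow-up wear days: 7 × 2 = 14 of 7 × 3 = 21.
- Follow-up wear periods in total: 2 × 25 = 50 to 2 × 30 = 60 at enrolment numbers; 2 × 20 = 40 to 2 × 24 = 48 at 80% retention.
- The August mid-point had passed by the 11/1/2020 note. For that version, half of these periods (25 to 30 at enrolment numbers) could only be recorded, not replanned.

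**Does the text cut off the monitor?**
- The event at which monitors were collected is replaced by mail and telephone. Section 11 does not confine mail to questionnaires; the survey wording is in the shorter notes in Sections 7 and 8.
- Participants receive instructions for putting the device on and taking it off, so no staff visit is needed to wear it.
- The wear protocol itself did not have to change, which is consistent with its absence from a list of changed items. It does not prove that the devices were posted.

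**Does a listed endpoint disappear?**
- Section 6 names physical activity, not an instrument. Godin is collected at follow-up, so the endpoint has 20 to 24 pairs at the retention floor whether or not monitors came back.
- Objective activity has about the same number of pairs if monitors were returned and 0 if they were not.

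**The case for a change.** The best argument for a change is that the COVID-19 text is otherwise detailed. It goes as far as sealing the diet show cards in an envelope, so silence on sending out and returning a device is noticeable. No sentence ties mail to the monitor. Section 32 says the monitors are used to measure outcomes and calls them the gold standard for sedentary behaviour and ambulation. Godin appears among the questionnaires mailed before baseline and is given by telephone at follow-up, so a Godin-only change could mix a change of mode with a change of behaviour. One added bullet would cost almost nothing.

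Much of this stands as description. The return route is unstated, and posting is an inference. The mode change is a fair caution when reading the Godin result.

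It does not amount to a reason to change the plan. The proposed bullet would record which of two things was done, posting or dropping follow-up wear, and staff had to settle that in running the study. It would not remove the Godin mode change, which exists either way. It could not restore performance testing, and it came too late to alter the mid-point. Section 32 describes the monitor's targets as sedentary behaviour and light activity; sedentary behaviour is not in the Section 6 list.

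**Conclusion.** No change is needed. The performance part is a missing cross-reference to an openly stated and explained omission: 0 pairs, with physical functioning still estimable from PROMIS-57. The monitor part is a logistic detail left unwritten for 2 wear periods per participant. It is not evidence that data were lost.

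This rests on two points. First, posting the devices is taken as the natural reading of a visit replaced by mail, for a device participants apply themselves; the documents neither confirm nor exclude it. Second, physical activity in Section 6 is taken as neutral on instrument, so Godin meets it. If follow-up wear was in fact dropped, objective activity is baseline-only, and the analysts would see this in the data and report it so. Even then the effect is confined to part of one secondary endpoint in a single-arm feasibility study with no power calculation. The adaptation, recruitment, retention, adherence and acceptability endpoints do not depend on it.
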